6.3 Pharmacokinetic Assessments

Venous blood samples will be collected daily from Day 1 through Day 7, Day 8, Day 9, and on Day 14 at the following time points to determine the plasma concentrations of REL-1017:

- PK sampling will be done on Day 1 at 1 hour pre-dose and 0.5, 1, 2, 4, 6, 8, and 12 hours post-dose.
- On Day 2 through Day 7, sampling will be done 1 hour pre-dose.
- On Day 8, sampling will be done approximately 24 hours after the last dose of study drug (on Day 7).
- On Day 9, sampling will be done approximately 48 hours after the last dose (on Day 7).
- On Day 14, sampling will be done approximately 168 hours after the last dose (on Day 7 ± 3 days).

A safety catheter will be placed before dosing on Day 1 until the 12-hour post-dose sample has been collected in the event a rescue medication is required.

Samples will be collected, processed, and shipped according to the site's SOPs and instructions from the Sponsor or the bioanalytical laboratory. The blood volumes required for PK sampling are available in Appendix 11.1.

The plasma samples will be analyzed by the bioanalytical laboratory using validated methods.

Plasma samples will be shipped frozen on dry ice from the research site to the bioanalytical laboratory. Samples will not be shipped without prior arrangement with the bioanalytical laboratory and notification of the Sponsor.

Drug concentration information that may unblind the study will not be reported to the study site or blinded personnel until the study has been unblinded.

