2.2 Secondary Objectives

The secondary objectives of this study are:

2.2.1 Pharmacokinetics:

The PK objective will characterize the PK profile of 25 mg and 50 mg of REL-1017 (d-methadone) as adjunctive treatment in patients with MDD. The PK profile of REL-1017 25 mg and 50 mg will be evaluated on Day 1 through Day 7, Day 8, Day 9, and Day 14 where the data allow:

- Maximum observed plasma concentration (C_{max})
- Time to maximum observed plasma concentration (T_{max})
- Area under the plasma concentration-time curve from time zero until the dosing interval of 24 hours (AUC_{tau})
- Area under the plasma concentration-time curve from time zero until the last quantifiable time point (AUC_{0-last}) on Day 7
- Area under the plasma concentration-time curve from time zero to infinity (AUC_{0-inf})
- Apparent termination elimination rate constant (λ_z)
- Apparent terminal elimination half-life ($t_{1/2}$)

- Attainment of steady state
- Steady state clearance (C_{SS}/F)
- Volume of distribution at steady state (V_{SS}/F)
- Accumulation ratios based on minimum observed plasma concentration (C_{min}), C_{max} , and AUC_{τ}

2.2.2 Efficacy:

The efficacy of 7 days of daily dosing with REL-1017 25 mg and 50 mg will be measured with the following efficacy endpoints:

- Change from Baseline (Day 1) to End of the Dosing Period (EDP, Day 7) on the Montgomery-Asberg Depression Rating Scale (MADRS) with measurements made pre-dose on Day 1 and Day 2; post-dose on Day 4 and Day 7 within 3 hours of dosing; and on Day 14;
- Change from Baseline (Day 1) to EDP (Day 7) on the Symptoms of Depression Questionnaire (SDQ) with measurements made pre-dose on Day 1 and Day 2; post-dose on Day 4 and Day 7 within 3 hours of dosing; and on Day 14; and,
- Change from Baseline (Day 1) to EDP (Day 7) on the Clinical Global Impressions of Severity (CGI-S) with measurements made pre-dose on Day 1 and Day 2; post-dose on Day 4 and Day 7 within 3 hours of dosing; and on Day 14.
- Evaluation of Clinical Global Impressions of Improvement (CGI-I) total score on Day 7 (post-dose), as well as CGI-I scores on Days 2 (pre-dose), 4 (post-dose), and 14.

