8 DATA ANALYSIS AND STATISTICAL CONSIDERATIONS

8.1 Statistical and Analytical Plans

8.1.1 Analysis Populations

The study analysis populations will consist of

- Randomized population: All patients who are randomized.
- Safety population: All randomized patients who receive any study treatment (REL-1017 or Placebo).
- Pharmacokinetic population: All patients who receive REL-1017, with at least 1 post-dose blood draw to determine plasma concentration of d-methadone. Pharmacokinetic parameters will be reported for this population where available.
- Intent-to-Treat population: All randomized patients who receive any study treatment (REL-1017 or Placebo) and have a Baseline and at least 1 post-Baseline efficacy measurement (MADRS, SDQ, CGI-S, or CGI-I).

The details of patient evaluability criteria will be determined prior to study unblinding.

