8.1.2 General Statistical Considerations

Complete details of the statistical analyses to be performed will be documented in a Statistical Analysis Plan (SAP) that will be completed prior to unblinding the study data. This document will include more details of the analysis populations, summary strategies, and any amendments to the proposed analyses listed here, if necessary. Any changes to the SAP will be outlined in the final clinical study report.

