8.1.3.2 Secondary Objective: Pharmacokinetic Profile of REL-1017

A secondary objective is to evaluate the PK profiles of 7 days of daily dosing with REL-1017 25 mg and 50 mg on Day 1 through Day 7, Day 8, Day 9, and Day 14 where data allow. The plasma concentration of d-methadone as a function of time will be analyzed using non-compartmental, validated software to estimate the following PK parameters:

- Maximum observed plasma concentration (C_{max})
- Time to maximum observed plasma concentration (T_{max})
- Area under the plasma concentration-time curve from time zero until the dosing interval of 24 hours (AUC_{tau})
- Area under the plasma concentration-time curve from time zero until the last quantifiable time point (AUC_{0-last})
- Area under the plasma concentration-time curve from time zero to infinity (AUC_{0-inf})
- Apparent termination elimination rate constant (λ_z)
- Apparent terminal elimination half-life ($t_{1/2}$)
- Attainment of steady state
- Steady state clearance (C_{SS}/F)
- Volume of distribution at steady state (V_{SS}/F)
- Accumulation ratios based on minimum observed plasma concentration (C_{min}), C_{max} , and AUC_{tau}

In addition, other relevant parameters may be calculated.

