8.1.4.4 Analysis of Pharmacokinetics

Blood samples will be collected for PK analysis on:

- Day 1 at 1 hour pre-dose (Baseline) and 0.5, 1, 2, 4, 6, 8, and 12 hours post-dose;
- Day 2 through Day 7 at 1 hour pre-dose;
- On Day 8 at 24 hours after the last dose of study drug (Day 7);
- On Day 9 at 48 hours after the last dose of study drug (Day 7) prior to Discharge from the CRU; and,
- On Day 14 at approximately 168 hours (\pm 3 days) after the last dose of study drug on Day 7.

The PK parameters for REL-1017 determined by non-compartmental analysis will be summarized. Graphs of the concentration (original and log transformed) versus time will be generated. Descriptive statistics, including number of patients, mean, standard deviation (SD), coefficient of variation (CV), median, minimum, and maximum, will be calculated by time point for REL-1017 25 mg and 50 mg. Concentrations below the limit of quantification (BLQ) will be set to zero for the generation of summary statistics for concentrations and the generation of mean concentration-time plots.

For the calculation of the PK parameters, concentration-time data will be treated as follows: BLQ concentrations prior to the first quantifiable concentration will be set to zero; BLQ concentrations after the first quantifiable concentration will be treated as missing; and pre-dose sampling times relative to dosing will be set to zero. Descriptive statistics, including number of patients, mean, SD, geometric mean, geometric CV, minimum, maximum, and median will be calculated for all REL-1017 PK parameters except T_{max} or $t_{1/2}$. The T_{max} data will be summarized with number of patients, minimum, maximum, and median. The $t_{1/2}$ data will be summarized with number of patients, mean, SD, minimum, maximum, and median.

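### The PK schedule takes no sample between the Day 7 dose and about 24 h, so it does not properly support the listed steady-state clearance and volume, Day 7 AUC0-last, or Cmax- and AUCtau-based accumulation ratios; the protocol also leaves the accumulation ratio undefined under a loading dose

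*Combined protocol and SAP*

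**What the plan says.** Sections 6.3 and 8.1.4.4 give the same sampling schedule.

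- Day 1: 1 h pre-dose, then 0.5, 1, 2, 4, 6, 8 and 12 h post-dose.
- Days 2 to 7: "On Day 2 through Day 7, sampling will be done 1 hour pre-dose".
- After the Day 7 dose: about 24 h (Day 8), 48 h (Day 9) and 168 h (Day 14, with a window of ±3 days).

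The Synopsis, section 2.2.1 and section 8.1.3.2 list the parameters: Cmax, Tmax, AUCtau, AUC0-last, AUC0-inf, the terminal rate constant and half-life, attainment of steady state, and steady-state clearance and volume. The last item is "Accumulation ratios based on minimum observed plasma concentration", and on Cmax and AUCtau as well. The Synopsis and section 2.2.1 tie AUC0-last to Day 7. Section 8.1.3.2 says that concentrations "will be analyzed using non-compartmental, validated software to estimate the following PK parameters".

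Two qualifiers apply. The profile is evaluated on Days 1 to 7, "Day 8, Day 9, and Day 14 where the data allow", and in section 8.1.1 "Pharmacokinetic parameters will be reported for this population where available".

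Two data rules in section 8.1.4.4 matter here: "pre-dose sampling times relative to dosing will be set to zero", and "BLQ concentrations after the first quantifiable concentration will be treated as missing".

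The Synopsis and sections 3.2 and 5.4 give the doses as 75 mg on Day 1 then 25 mg (Arm 1), and 100 mg on Day 1 then 50 mg (Arm 2).

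**The concern.** Several listed parameters need the shape of the curve after a late dose, and the schedule collects none of it. Steady-state clearance by non-compartmental methods is normally dose over AUCtau at steady state. An accumulation ratio on Cmax or AUCtau needs a late Cmax or AUCtau. Day 7 AUC0-last needs the first 24 h after the Day 7 dose. All of these would have to come from a trough before that dose and a trough after it.

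Because the pre-dose time is set to zero, software will return a Day 7 AUCtau from those two points. Nothing in the text screens out a value that is computable but biased.

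The second problem is the accumulation ratio. Under a loading dose, a ratio of a late day to Day 1 compares different doses. Without a reference day and dose normalisation, the number describes how the loading regimen settled and not how the drug accumulates at a fixed dose. Section 1.2.2 reports accumulation under constant dosing in the earlier 10-day study, and a reader might set the two side by side.

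**Working it through.** **1. Count of samples (no model).** Take the Day 1 dose as 0 h and the Day 7 dose as 144 h. Scheduled draws strictly between 144 h and 168 h: none. Draws bounding that interval: 143 h (Day 7 pre-dose) and 168 h (Day 8). Draws inside the Day 1 interval: 0.5, 1, 2, 4, 6, 8, 12 h and the Day 2 pre-dose sample at 23 h, so 8. Day 1 is well described and Day 7 is not.

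**2. Dose factor (no model).** 75/25 = 3 and 100/50 = 2. Any ratio of a Day 7 measure to a Day 1 measure changes by exactly 3 or 2 when both are divided by the preceding dose.

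**3. Illustration of size.** The protocol gives no figure to reproduce. Assumed, and not in the documents: one compartment, linear kinetics, half-life 20-40 h, ka 0.5-2 per h, no noise. With ke = ln 2 / half-life,

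C(t) = Σ D_j · ka/(ka − ke) · [exp(−ke(t − 24j)) − exp(−ka(t − 24j))], summed over doses j = 0 to 6 already given at t.

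Volume and bioavailability cancel in every ratio below.

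The 40 h limit comes from section 1.2.2, which reports steady state by Dose 7 at 25 and 50 mg. Without loading, the fraction of steady state reached before the Day 7 dose is 1 − exp(−144·ke): 0.993 at 20 h, 0.918 at 40 h, 0.811 at 60 h. The last fits poorly with that report.

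*One case, Arm 1, half-life 30 h, ka 1 per h.* C(143) = 35.95 and C(168) = 34.87. Two-trough AUCtau = 24 × (35.95 + 34.87)/2 = 849.9; the true area from 144 to 168 h is 1093.0. The ratio is 0.778, so clearance is overstated by 1/0.778 = 1.286. For troughs, C(23) = 45.13, so the raw ratio is 35.95/45.13 = 0.797. Dose-normalised it is 3 × 0.797 = 2.39. Constant dosing without loading gives 2.265, so carry-over is 2.390/2.265 − 1 = 5.5%.

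*Ranges over half-life 20-40 h:*

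| Quantity | Arm 1 | Arm 2 |
|---|---|---|
| Raw Cmin ratio, C(143)/C(23) | 0.60-0.98 | 0.89-1.41 |
| Dose-normalised (×3 or ×2) | 1.79-2.95 | 1.77-2.82 |
| Same-dose accumulation, no loading | 1.76-2.70 | 1.76-2.70 |
| Carry-over in the normalised ratio | 2-9% | 1-5% |

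For both arms together:

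- Two-trough over true Day 7 AUCtau: 0.664-0.843, so 16-34% low.
- Clearance as dose over AUCtau: 1.186-1.505 times the value from the true area, so 19-51% high.
- Higher Day 7 trough over true Day 7 Cmax: 0.488-0.755.

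**4. Day 7 AUC0-last.** Here the 48 h and 168 h samples also enter. Ratio to the true area over the same span:

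- To 168 h: 1.042-1.105 with the linear rule, 0.811-0.945 with linear-up/log-down.
- To 48 h only: 0.785-0.913 and 0.767-0.907.

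The sign depends on the trapezoid rule, which the protocol does not state, and on whether the 168 h sample is quantifiable. The 168 h level is 0.3-6% of the Day 7 Cmax in this model, so that is not assured.

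**The case against.** The strongest reply is that the plan never expressly promises a Day 7 Cmax, Tmax or AUCtau. Only AUC0-last is tied to Day 7, and section 8.1.3.2 omits even that. With the two qualifiers, the natural reading is Cmax, Tmax and AUCtau from Day 1 and steady state from troughs. This stands. A reader might infer that the plan commits to reporting a two-trough AUCtau, but no text says so. What remains are listed items with no proper source: steady-state clearance and volume, the Cmax and AUCtau accumulation ratios, and Day 7 AUC0-last.

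Second, section 8.1.2 defers full analysis detail to the SAP, whose text was not available. A reference day and dose normalisation may well be defined there, so the claim is only that the protocol does not state them. The SAP cannot supply samples that were never drawn. The text of the PK footnote to Table 1 was also not available, but two complete and matching schedules make a contrary footnote unlikely.

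Third, it is tempting to say that half-life fails if the 168 h sample is below quantification and so treated as missing. That goes too far. The 24 and 48 h samples remain, as does the Day 1 decline at 6, 8, 12 and 23 h. The estimate would be weak but not impossible.

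Fourth, the sizes rest on assumed kinetics, and no planned analysis compares accumulation ratios between arms or with the earlier study. Both points are fair.

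**Conclusion.** The point holds, at minor severity. The absence of a draw between the Day 7 dose and about 24 h, and the factors of 3 and 2, come straight from the documents. The percentages (AUCtau 16-34% low, clearance 19-51% high) show direction and scale only, under one-compartment linear kinetics with a half-life of 20-40 h and ka of 0.5-2 per h. No direction can be claimed for Day 7 AUC0-last.

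The qualifiers permit omission but do not identify what to omit, so they do not settle the matter. An unnormalised Arm 1 trough ratio would lie below 1 across the assumed range although same-dose accumulation is 1.76-2.70, and could be misread as no accumulation.

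A reader might infer that the PK objective as a whole fails. It does not. Day 1 Cmax, Tmax and AUCtau, Cmin, and attainment of steady state are unaffected. PK is a descriptive secondary objective, and no test or decision in the protocol depends on it.

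**What to change.** 1. State that non-compartmental Cmax, Tmax and AUCtau are from Day 1 only. Then either remove Day 7 AUC0-last, steady-state clearance and volume, and the Cmax and AUCtau accumulation ratios, or label them as model-based estimates from a population PK model using actual sampling times. If modelled, say that Day 7 peak values rest on Day 1 absorption data and the assumed structure.
2. Define accumulation on Cmin as Day 7 pre-dose over Day 2 pre-dose (both about 23 h after a dose), each divided by the preceding dose. Note the loading-dose carry-over of about 2-9% (Arm 1) and 1-5% (Arm 2) under the assumed model. Section 1.2.2 reports dose proportionality over 25-75 mg, so the linearity caveat bears mainly on the 100 mg Day 1 dose in Arm 2. Show an unnormalised ratio only if it is labelled as describing the loading regimen.
3. Use actual sampling times for the terminal rate constant and half-life, since the Day 14 draw can move by 3 days, and report them only where enough terminal samples are quantifiable.

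The cost is wording in the protocol and SAP, with no extra draws or visits. The price is fewer directly reported steady-state parameters, or modest modelling work.

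A separate clerical point: Appendix 11.1 counts 7 + 2 = 9 PK samples where section 6.3 requires 8 + 6 + 3 = 17, and its bracketed counts add to 4 + 3 + 11 + 4 = 22 against a stated 21. These should be reconciled.

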6.4 Efficacy Assessments

Efficacy assessments will be performed at the time points indicated in the Time and Events Schedule (Table 1).

6.4.1 Primary Efficacy Measure

The Montgomery-Asberg Depression Rating Scale (MADRS) will be measured at pre-dose on Day 1 and Day 2; post-dose on Day 4 and Day 7 within 3 hours of dosing; and on Day 14.

6.4.2 Secondary Efficacy Measures

6.4.2.1 Symptoms of Depression Questionnaire (SDQ)

The SDQ is a 44-item, self-report scale designed to measure the severity of symptoms across several subtypes of depression. The SDQ was developed to more fully capture the heterogeneity of symptom presentations of depressive disorders than current, widely used scales for MDD. The SDQ includes items that inquire about an extensive number of depressive symptoms beyond the ones included in other commonly used scales such as the Quick Inventory of Depression Symptomatology (QIDS).

The 44 SDQ items are rated on a 6-point scale. Each item is rated based on a subject's perception of what is normal for the individual (score = 2), what is better than normal (score = 1), and what is worse than normal (scores = 3–6).

Items reflect a broad and heterogeneous collection of depression related symptom features. For example, Factor 1 (see Appendix 11.9) measures common dimensions of depressive symptoms including lassitude, energy, mood, and cognitive, and social functioning (subscale 1). Factor 3 includes items on outlook on life, pessimism, suicide, self-harm, and worthlessness (subscale 3). Factors 4 and 5 measure physiological features of depression, namely sleep difficulties and changes in appetite/weight, respectively. Moreover, the SDQ includes several items that inquire about anxiety symptoms often present among depressed patients.³⁵

6.4.2.2 Clinical Global Impressions (CGI) Scale

The CGI-S will be measured at pre-dose on Day 1 and Day 2; post-dose on Day 4 and Day 7 within 3 hours of dosing; and on Day 14. The CGI-I will be measured at pre-dose on Day 2, post-dose on Day 4 and Day 7 within 3 hours of dosing, and on Day 14.

6.5 Pharmacogenetic Analysis

On Day 1 of dosing, a blood sample for DNA isolation will be collected from all patients in this study for potential pharmacogenetic analysis of genes that may affect the PK of d-methadone. Pharmacogenetic analysis may be performed in cases where patients experience abnormal PK results. This analysis would be restricted to the evaluation of genes that may be involved in the PK of d-methadone (e.g., drug metabolism, disposition, elimination).

One 4 mL whole blood sample for DNA isolation will be collected on Day 1 from each patient into an appropriately labeled ethylene diamine tetra-acetic acid (EDTA) tube. The tube will be inverted 8 to 10 times to reduce the chance of clot formation. Within 30 minutes of collection, the sample will be stored at -20°C or colder until shipped on dry ice sufficient to last during

transport. Samples will be collected and shipped according to the site's SOPs and instructions from the Sponsor and/or pharmacogenetic laboratory.

The samples will be stored in a secure space with adequate measures to protect patient confidentiality. The samples will be retained while research on d-methadone (REL-1017) continues, but not longer than 20 years.

6.6 Appropriateness of Measures

All safety and efficacy assessments have been well documented and are generally regarded as reliable, accurate, and relevant in this patient population.

6.6.1 Baseline Measurements

6.6.1.1 Mini International Neuropsychiatric Interview

The MINI, Version 7.0.2, is a widely used psychiatric structured diagnostic interview instrument that can be used to assess the effectiveness of the patient's prescribed antidepressant medication. The interview is brief and only requires "yes" or "no" answers.³⁶

6.6.1.2 Antidepressant Treatment Response Questionnaire

The ATRQ examines the efficacy and adequacy of any antidepressant treatment in a step-by-step procedure. This widely accepted questionnaire evaluates improvement (0% to 100%) and adequacy (adequate duration and dose).³⁷

6.6.1.3 Hamilton Depression Rating Scale (HAM-D-17)

The HAM-D-17 has proven useful for many years as a way of determining a patient's level of depression before, during, and after treatment. Many clinicians consider the HAM-D-17 to be the gold standard for evaluating the severity of a patient's depression. In Study REL-1017-202, the HAM-D-17 must be administered using the Structured Interview Guide for the Hamilton Depression Rating Scale (SIGH-D).³⁸

6.6.2 Efficacy Measurements

6.6.2.1 Montgomery-Asberg Depression Rating Scale (MADRS)

The MADRS is one of the questionnaires most frequently used in clinical studies to measure outcome in antidepressant efficacy studies. This scale exhibits construct validity (internal homogeneity) and concurrent validity relative to the HAM-D-17 and the concepts of endogenous and non-endogenous depression. The questionnaire includes questions on the following symptoms: (1) Apparent sadness; (2) Reported sadness; (3) Inner tension; (4) Reduced sleep; (5) Reduced appetite; (6) Concentration difficulties; (7) Lassitude; (8) Inability to feel; (9) Pessimistic thoughts; (10) Suicidal thoughts. A higher MADRS score indicates severer depression, and each item yields a score of 0 to 6. The overall score ranges from 0 to 60 with scores above 34 indicating severe depression. In Study REL-1017-202, the MADRS must be administered using the Structured Interview Guide for the MADRS (SIGMA).^{39, 40,41}

6.6.2.2 Clinical Global Impressions (CGI) Scale

The CGI-S is a standard method used in clinical studies to quantify and track patient progress

and treatment response over time. The scale is composed of 7 ratings: 1 = normal, not at all ill; 2 = borderline ill; 3 = mildly ill; 4 = moderately ill; 5 = markedly ill; 6 = severely ill; and 7 = among the most extremely ill patients. The score ranges from 1 to 7, and a lower CGI-S score indicates lower levels of depression.⁴²

The CGI-I is a standard method used in clinical studies to quantify and track patient change over time. The scale is composed of 7 ratings: 1 = very much improved; 2 = much improved; 3 = minimally improved; 4 = no change; 5 = minimally worse; 6 = much worse; and 7 = very much worse. The score ranges from 1 to 7, and a lower CGI-I score indicates greater improvement in symptoms.⁴²

